- ^a. Patients will be followed in two exposure categories, rivaroxaban or SOC (heparins, VKAs, other DOACs). Treatment episode of rivaroxaban oral suspension OR SOC defined by cumulative days of supply from consecutive dispensations, until discontinuation (grace period of 30 days allowed and 30-day carry-over period) or switch to other anticoagulation therapy. During an anticoagulation treatment period, switches from SOC to rivaroxaban and vice versa are allowed.
- ^b. Baseline conditions: demographics, characteristics of the index VTE, co-morbidities, prior treatment.
- ^c. Censoring criteria will be the earliest of: discontinuation of all study drugs (rivaroxaban and SOC), death, disenrollment/de-registering/emigration, last available data, end of the study period.

Adapted from Schneeweiss S et al. Graphical Depiction of Longitudinal Study Designs in Health Care Databases. *Ann Intern Med.* 2019 Mar 19;170(6):398-406.

Figure 1 Study design diagram

The strengths of this study design to answer the research question include:

- Use of population-based secondary health data sources which capture observational data from routine clinical practice. This avoids the possibility to influence prescribing behaviour and reduces the risk of selection bias or recall bias due to the secondary nature of the data. The results will reflect prescribing behaviour and risk of outcomes in real-world clinical practice.
- Selection of secondary health data sources providing large population coverage and/or population size, as well as broad coverage of health care settings from different geographical locations and health care systems. This will help: i) maximizing study size in this rare clinical condition, ii) providing ability to identify and follow-up the study population by capturing relevant diagnoses, drugs, and outcomes, and iii) ensuring representativeness for the general target population.
- Use of a new user design, where the at-risk period begins on the date of first observed record of anticoagulation therapy (index date), instead of the preceding VTE date.
- Contextualization of the use of and outcomes with rivaroxaban oral suspension by available contemporary treatment options.

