9.3.2.2.2. Effectiveness outcome

A secondary outcome on effectiveness will be recurrent symptomatic VTE.

Potential cases will be identified using diagnostic codes according to the different coding systems in the data sources (preliminary list in [Annex 3](#)). Care for children with an incident VTE takes place in inpatient setting (i.e., hospital stay requiring at least one night). At the same time, it is highly likely that VTE diagnoses are recorded as complications, secondary to other main reasons for a hospital stay. Therefore, the main definition for VTE diagnoses will be based on a sensitive approach including all primary/main and secondary diagnoses captured during hospitalization. Thus, a case of recurrent symptomatic VTE will be defined as a hospitalization with one of the following primary, related or associated diagnoses:

- DVT
- PE
- Cerebral vein or sinus thrombosis
- Central venous catheter related thrombosis
- Any VTE resulting in death.

A sensitivity analysis is planned for VTE outcome with a more restrictive definition using only main/primary diagnostic codes, excluding secondary diagnostic codes.

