Sweden	MBR, NPR, PDR, Cause of death register	National health registers	10.3 million	100%	14 days-12 months	ATC	Prescribed drugs for outpatient use, dispensed drugs through retail pharmacies, use of OTC drugs, reimbursed drugs	ICD-10	Inpatient care and specialized outpatient care
France	SNDS	Claims database	66 million	99%	3-7 months	ATC, UCD, CIP	Dispensed drugs through retail pharmacies, reimbursed drugs, some costly drugs administered in hospital	ICD-10	Inpatient care, some ambulatory long-term diseases, all procedures
Spain (Catalonia)	SIDIAP	EMR database	5.6 million	74% (from Catalonia)	12 months	ATC	Primary care prescriptions, drugs dispensed through retail pharmacies. Possible linkage with hospital pharmacy drugs databases	ICD-9, ICD-10-CM	Primary care linked to hospital admissions and deaths

ATC = Anatomical Therapeutic Chemical (Classification System); CIP = Club Inter-Pharmaceutique; CM = Clinical Modification; EMR = Electronic Medical Records; ICD = International Classification of Diseases; MBR = Medical Birth Register; NPR = National Patient Register; PDR = Prescribed Drug Register; RMPS = Register of Medicinal Products Statistics; SIDIAP = Sistema d'Informació per al Desenvolupament de l'Investigació en Atenció Primària; SNDS = Système National Des Données De Santé; SMR = Hospital Patient Medication Register; UCD = Unité Commune de Dispensation.

The feasibility of study objectives is summarized in [Table 4](#).

Table 4: Feasibility of study objectives in the data sources

Data sources	Danish national registers	SNDS	SIDIAP	Swedish national registers
Primary objectives				
To describe clinical characteristics and demographics of patients using anticoagulation therapy for the treatment of VTE (rivaroxaban oral suspension or SOC)	Yes	Yes	Yes	Yes
To describe use of anticoagulation therapy (including selected drug, dose, and duration) for treatment of VTE	Yes ^a	Yes	Yes ^a	Yes
To describe the incidence and severity of bleeding (major bleeding, and CRNM bleeding) according to anticoagulation therapy (rivaroxaban oral suspension or SOC)	BT ^b	Yes	BT ^b	BT ^b
Secondary objectives				
To describe time trends in patient characteristics and anticoagulation treatment patterns at the population-level over the study period	Yes ^a	Yes	Yes ^a	Yes
To describe the incidence of recurrent symptomatic VTE according to anticoagulation therapy (rivaroxaban oral suspension or SOC)	BT ^b	BT ^b	BT ^b	BT ^b

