9.9. Limitations of the research methods

The use of secondary data that has not been primarily collected for research purposes comes with specific limitations.

Selection bias

- All patients fulfilling eligibility criteria will be included in the study. The data sources in the different countries differ in terms of contents and expected coverage. Most have a national coverage, while SIDIAP which only covers ~75% of Catalonia is also considered representative of the Spanish population. Therefore, the selection bias is considered to be low with respect to the target countries.

Information bias

- Exposure data
 - Anticoagulation therapy is expected to be initiated during hospital stay and renewed for outpatient use. According to its indication, rivaroxaban oral suspension should be used after at least five days of initial parenteral anticoagulation treatment. Thus, in theory, all patients receiving rivaroxaban should be switchers from parenteral anticoagulant treatment. In practice, the capacity to observe the actual initial parenteral anticoagulation treatment and its duration will depend on the availability of inpatient drug data in the selected data sources. This will be feasible when

inpatient drug data is captured, e.g., in the Danish SMR (soon available, with data collected since May 2018) and in SIDIAP through linkage with hospital dispensation medication. However, inpatient drug data is not captured in SNDS and in Swedish national registers, which represents a risk of exposure underestimation. In this latter situation, the information on anticoagulation therapy and its duration will be based on outpatient prescriptions only, at a time when patients may have already, or not yet, stopped the initial parenteral anticoagulation treatment, and switched to maintenance therapy like rivaroxaban. Hence, when patients will have switched to rivaroxaban during hospital stay in an unobservable period in the data source, they will appear as initiating anticoagulation therapy with rivaroxaban, and not switchers. To avoid immeasurable time bias, the index date will be the first observed record of anticoagulation therapy in each data source, whether it occurs during inpatient stay or afterwards.

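### In SNDS, the one source where bleeding is expected to be reportable, follow-up starts at the first outpatient fill, so earlier bleeds and children who never reach a fill are lost and the new-user claim does not hold

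*Protocol*

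**What the plan says.** Among the design strengths, Protocol Section 9.1 lists: "Use of a new user design, where the at-risk period begins on the date of first observed record of anticoagulation therapy (index date". The abstract also describes a cohort of new users. Section 9.2.3.1 defines initiation as a first anticoagulant record with none in the preceding six months, or since birth in younger infants. Section 9.2.2.1 starts follow-up at the index date.

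On where treatment begins, Section 9.3.2.2.2 says: "Care for children with an incident VTE takes place in inpatient setting". Section 9.9 says: "Anticoagulation therapy is expected to be initiated during hospital stay and renewed for outpatient use".

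On the data, Section 9.9 says: "inpatient drug data is not captured in SNDS and in Swedish national registers, which represents a risk of exposure underestimation". In those sources, "the information on anticoagulation therapy and its duration will be based on outpatient prescriptions only". It then gives the index rule, "the index date will be the first observed record of anticoagulation therapy in each data source, whether it occurs during inpatient stay or afterwards", and presents it as a guard against immeasurable time bias. The selection-bias paragraph of the same section discusses how much of each country the databases cover and concludes that selection bias is low.

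Sections 9.5.2, 9.7.8 and 9.9 expect the bleeding analysis to be feasible only in SNDS. Section 6 is slightly looser and speaks of the largest source or sources.

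**The concern.** A new-user design is valued because it observes patients from the first dose, so that early events are counted and nobody is selected for having come through the early period. If the first doses are given in hospital and the database cannot see them, the first observed record belongs to a child who is already treated, has survived and is still anticoagulated at the first outpatient fill.

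The study was requested to address bleeding risk in very young children (Section 7.1). If its bleeding result comes from SNDS alone, that result describes bleeding after the first outpatient dispensing. A reader of the report would take it as bleeding since the start of therapy. The cumulative incidence planned at 3, 6, 9 and 12 months (Section 9.7.4) has the same problem, because its time zero is the first fill. The exploratory contrast between rivaroxaban and SOC is also affected if the first fill falls at different points of the treatment course in the two categories.

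**Working it through.** **1. When time at risk starts in SNDS.** The chain uses only the protocol's statements:
- Incident VTE is treated in hospital (Section 9.3.2.2.2), and anticoagulation is expected to start there (Section 9.9).
- SNDS and Sweden do not record inpatient anticoagulants; exposure rests on outpatient prescriptions (Section 9.9).
- The index date is the first observed record (Sections 9.1 and 9.9), and follow-up runs from it (Section 9.2.2.1).

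Time zero in these two sources is therefore the first outpatient fill. The six-month washout cannot be verified for the hospital stay itself.

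**2. What is lost.**
- A bleed between the first in-hospital dose and the first fill precedes time zero and is not an outcome.
- A child who dies, or whose anticoagulant is stopped, before any fill has no anticoagulant record and fails the initiation criterion.
- The VTE code must fall in the 30 days before the index date (Section 9.2.3.1). A child whose first fill comes more than 30 days after the last inpatient VTE code is also not eligible.

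**3. Whether other parts of the plan recover this.** The sensitivity analyses in Section 9.7.6 change the carry-over rule and restrict bleeding and VTE to main diagnoses. None changes the start of follow-up. The bleeding limitations in Section 9.9 concern coding and severity. Denmark and SIDIAP can have inpatient drug data, but their expected bleeding counts are below the disclosure threshold (Table 4).

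**4. The protocol's own SNDS projection (Section 9.5.2, Table 6).**
- Sum of yearly market shares: 0.10 + 0.32 + 0.38 + 0.42 + 0.50 + 0.30 = 2.02.
- Rivaroxaban children: 650 / 6 × 2.02 = 218.8 (stated 219).
- Rivaroxaban bleeds: 219 × 0.056 = 12.3 (stated 12).
- All bleeds: 12.3 + (650 − 219) × 0.059 = 12.3 + 25.4 = 37.7 (stated 37).

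The figures reproduce to within rounding. The trial incidence is applied with no term for the period before the first fill.

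**5. How much of the study is affected.**
- SNDS: 650 / 846 = 77% of children and 219 / 285 = 77% of rivaroxaban children.
- SNDS plus Sweden: (650 + 98) / 846 = 88% and (219 + 33) / 285 = 88%. Sweden's bleeding count is expected to be suppressed in any case, so 77% is the relevant figure for the bleeding objective.

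**6. Direction of the effect on the rate.** Let E events and T person-time accrue over the full course among children who enter, with E0 and T0 falling before the first fill. The study sees (E − E0) / (T − T0). This is below E / T only if E0 / T0 exceeds E / T, that is, only if the pre-fill bleeding rate is above the overall rate. The protocol gives no bleeding rate by time since start, and no count of children who never reach a fill. Neither sign nor size can be derived.

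**The case against.** Much of the data limitation is disclosed. Section 9.1 words new use as the first observed record. Section 9.2.3.1 says the observed first drug may differ from the one actually received, and Section 9.9 says that switchers will appear as initiators. The index rule is credited only with avoiding immeasurable time bias, and it does keep unobservable inpatient time out of the denominator. No better index date exists in SNDS, and comparisons are exploratory (Section 9.7.1). All of this stands. It makes the problem one of labelling and reporting; it does not supply the missing statement about bleeds and cohort entry.

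Two details narrow the point. Table 3 lists some costly hospital drugs for SNDS, but it names no anticoagulant and Section 9.9 treats inpatient drugs as not captured. The loss is exact only before the first fill: a child already indexed who switches to rivaroxaban during a later stay and bleeds is counted, under the earlier category.

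A reader might infer more than the documents support:
- **That bleeding risk is understated.** Person-time is removed along with events (step 6), so this needs a higher early rate that no section reports.
- **That the 12 expected rivaroxaban bleeds should be scaled down by an assumed in-hospital share.** No share is given. Under the as-treated rule, bleeds on lead-in heparin belong to SOC, so one share cannot be applied to the rivaroxaban count. The protocol also does not say whether the reference trial's incidence includes lead-in bleeds.
- **That Table 4 is wrong to rate bleeding feasible in SNDS.** The contrasting entries in that row mark counts below the disclosure threshold. The row says nothing about completeness of early follow-up.
- **That rates should be split by time since discharge.** About 12 rivaroxaban bleeds are expected (range 5 to 20) and France suppresses counts below 10. Any two-way split of 12 leaves at least one part at 6 or fewer.

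**Conclusion.** The concern holds in limited form. In SNDS, with 77% of expected children and the only expected bleeding result, the cohort consists of children with an observed outpatient fill, followed from that fill. It is not a new-user cohort in the usual sense. Selection bias cannot be called low on the ground of database coverage alone, because entry depends on surviving and remaining anticoagulated until a fill. The same applies to Sweden. Section 9.9 covers the exposure side and leaves out the consequences for bleeding and for entry.

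This rests on the protocol's own statements that treatment starts in hospital and that inpatient drugs are not captured, and on its expectation that only SNDS can report bleeding. No direction or size of bias is claimed. The point changes what the SNDS estimate may be called and what can be concluded from it; it does not invalidate the analysis.

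**What to change.** **Wording.**
- In Section 9.1 and the abstract, limit the new-user description to sources with inpatient drug records.
- Name the SNDS and Swedish outcome *bleeding after first outpatient dispensing following the VTE stay*.
- State that cumulative incidence there is measured from the first fill, and limit conclusions accordingly.
- In Section 9.9, correct the selection-bias paragraph. State that bleeds before the first fill are not counted and that children who die or stop treatment before a fill do not enter.

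**Two descriptive additions from hospital-discharge data, which these sources already contain (Section 9.4.2, Annex 3).**
- The number of cohort children with a bleeding code in the index VTE stay.
- In the attrition table already planned in Section 9.7.2, the number of VTE stays in children under two with no outpatient anticoagulant fill within 30 days, with in-hospital deaths and bleeding codes where counts permit.

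**Cost.** Text edits, a small table, and an extraction that keeps VTE stays without a fill. The counts have limits that should be printed with them. They cannot be attributed to a drug, and a bleeding code may precede the VTE or the anticoagulant. Stays without a fill include children who were never anticoagulated. Counts below the disclosure limit (10 in France, 5 in Sweden) will be suppressed.

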9.10. Other aspects

Not applicable

10. Protection of human subjects

The analysis for this study is based on secondary data use. No identifying data will be collected in any of the planned approaches.

The study will be conducted in agreement with the regulation (EU) 2016/679 of the European Parliament on the protection of natural persons with regard to the processing of personal data and on the free movement of such data (GDPR).

Regulatory and ethical requirements will be followed in each country where the respective countries databases are used. The study will comply with the module VIII of the good pharmacovigilance practices (GVP).

Although EU Pharmacovigilance Directive (DIR 2010/84/EU) is a legal act, it does not carry the same binding force of a regulation; each Member State can determine how best to transpose the Directive into local legislation. As a result, the submission requirements for PASS vary throughout the EU, with some countries being more onerous than others. The project team will include experts that are dedicated to the review and advisement on the regulations and guidelines applicable to this study in the participating countries.

The study will be submitted to ethical review boards (ERBs) for approval wherever required by local laws. Regulatory authorities will be notified, and approval sought as required by local laws and regulations. Annual progress reports will be submitted to ERBs, and regulatory authorities as required by local laws and regulations.

11. Management and reporting of adverse events/adverse reactions

This study is based on the secondary use of data from the country-specific databases.

As per the EMA Guideline on GVP (Module VI–Management and reporting of adverse reactions to medicinal products [Revision 1]), individual reporting of adverse reactions is not required for non-interventional study designs that are based on secondary use of data (20).

12. Plans for disseminating and communicating study results

This study will be registered at “www.clinicaltrials.gov” and in the EU PAS register at “http://www.encepp.eu/encepp_studies/indexRegister.shtml”.

Annual progress reports and – at study completion – a final report will be sent to the EMA.

The final report will follow the structure recommended in the EMA template “Guidance for the format and content of the final study report of non-interventional post-authorisation safety studies”(21).

Annex 1: List of stand-alone documents

Document Name

- *22195_Feasibility Report, v 1.0, 15-APR-2022*
- *22195_Steering Committee Charter, v 0.1, 03-MAR-2022*
- *22195_Study timelines and milestones tracker: Study tracked in Mont Blanc*
- *22195_Detailed list of variables: Not yet available, additional information in Annex 3*
- *22195_SAP: Not yet available*

Annex 2: ENCePP checklist for post-authorization safety study (PASS) protocols**ENCePP Checklist for Study Protocols (Revision 4)**

Adopted by the ENCePP Steering Group on 15/10/2018

Study title: Xarelto Paediatric VTE PASS Drug Utilization Study: An observational, longitudinal, multi-source drug utilization safety study to evaluate the drug use patterns and safety of rivaroxaban oral suspension in children under two years with venous thromboembolism (XAPAEDUS)

EU PAS Register® number: Study not yet registered
Study reference number (if applicable):

Section 1: Milestones	Yes	No	N/A	Section Number
1.1 Does the protocol specify timelines for				6
1.1.1 Start of data collection ¹				
1.1.2 End of data collection ²				
1.1.3 Progress report(s)				
1.1.4 Interim report(s)				
1.1.5 Registration in the EU PAS Register®				
1.1.6 Final report of study results.				

Comments:

--

Section 2: Research question	Yes	No	N/A	Section Number
2.1 Does the formulation of the research question and objectives clearly explain:				
2.1.1 Why the study is conducted? (e.g., to address an important public health concern, a risk identified in the risk management plan, an emerging safety issue)				7
2.1.2 The objective(s) of the study?				8
2.1.3 The target population? (i.e., population or subgroup to whom the study results are intended to be generalised)				9.2.1, 9.2.4
2.1.4 Which hypothesis(-es) is (are) to be tested?				

¹ Date from which information on the first study is first recorded in the study dataset or, in the case of secondary use of data, the date from which data extraction starts.

² Date from which the analytical dataset is completely available.

Section 2: Research question	Yes	No	N/A	Section Number
2.1.5 If applicable, that there is no a priori hypothesis?				9.5

Comments:

--

Section 3: Study design	Yes	No	N/A	Section Number
3.1 Is the study design described? (e.g., cohort, case-control, cross-sectional, other design)				9.1
3.2 Does the protocol specify whether the study is based on primary, secondary or combined data collection?				9.1, 9.4
3.3 Does the protocol specify measures of occurrence? (e.g., rate, risk, prevalence)				9.7
3.4 Does the protocol specify measure(s) of association? (e.g., risk, odds ratio, excess risk, rate ratio, hazard ratio, risk/rate difference, number needed to harm (NNH))				
3.5 Does the protocol describe the approach for the collection and reporting of adverse events/adverse reactions? (e.g., adverse events that will not be collected in case of primary data collection)				11

Comments:

--

Section 4: Source and study populations	Yes	No	N/A	Section Number
4.1 Is the source population described?				9.2.1
4.2 Is the planned study population defined in terms of:				
4.2.1 Study time period				9.2.2
4.2.2 Age and sex				9.2.1, 9.2.3
4.2.3 Country of origin				9.1
4.2.4 Disease/indication				9.2.1, 9.2.3
4.2.5 Duration of follow-up				9.2.2
4.3 Does the protocol define how the study population will be sampled from the source population? (e.g., event or inclusion/exclusion criteria)				9.2.4

Comments:

--

Section 5: Exposure definition and measurement	Yes	No	N/A	Section Number
5.1 Does the protocol describe how the study exposure is defined and measured? (e.g., operational details for defining and categorising exposure, measurement of dose and duration of drug exposure)				9.3.1
5.2 Does the protocol address the validity of the exposure measurement? (e.g., precision, accuracy, use of validation sub-study)				9.2.3, 9.9
5.3 Is exposure categorised according to time windows?				9.1, 9.3.1
5.4 Is intensity of exposure addressed? (e.g., dose, duration)				9.3.1
5.5 Is exposure categorised based on biological mechanism of action and taking into account the pharmacokinetics and pharmacodynamics of the drug?				9.3.1
5.6 Is (are) (an) appropriate comparator(s) identified?				9.1, 9.3.1

Comments:

--

Section 6: Outcome definition and measurement	Yes	No	N/A	Section Number
6.1 Does the protocol specify the primary and secondary (if applicable) outcome(s) to be investigated?				9.3.2
6.2 Does the protocol describe how the outcomes are defined and measured?				9.3.2
6.3 Does the protocol address the validity of outcome measurement? (e.g., precision, accuracy, sensitivity, specificity, positive predictive value, use of validation sub-study)				9.3.2, 9.4, 9.9
6.4 Does the protocol describe specific outcomes relevant for Health Technology Assessment? (e.g., HRQoL, QALYs, DALYS, health care services utilisation, burden of disease or treatment, compliance, disease management)				9.3.2.1.1

Comments:

--

Section 7: Bias	Yes	No	N/A	Section Number
7.1 Does the protocol address ways to measure confounding? (e.g., confounding by indication)				
7.2 Does the protocol address selection bias? (e.g., healthy user/adherer bias)				9.1, 9.9

22195; XAPAEDUS; v 2.1, 16 NOV 2022;

Page 49 of 59

based on template version 9

Section 7: Bias	Yes	No	N/A	Section Number
7.3 Does the protocol address information bias? (e.g., misclassification of exposure and outcomes, time-related bias)				9.9

Comments:

--

Section 8: Effect measure modification	Yes	No	N/A	Section Number
8.1 Does the protocol address effect modifiers? (e.g., collection of data on known effect modifiers, subgroup analyses, anticipated direction of effect)				

Comments:

--

Section 9: Data sources	Yes	No	N/A	Section Number
9.1 Does the protocol describe the data source(s) used in the study for the ascertainment of:				
9.1.1 Exposure? (e.g., pharmacy dispensing, general practice prescribing, claims data, self-report, face-to-face interview)				9.4
9.1.2 Outcomes? (e.g., clinical records, laboratory markers or values, claims data, self-report, patient interview including scales and questionnaires, vital statistics)				9.4
9.1.3 Covariates and other characteristics?				9.4
9.2 Does the protocol describe the information available from the data source(s) on:				
9.2.1 Exposure? (e.g., date of dispensing, drug quantity, dose, number of days of supply prescription, daily dosage, prescriber)				9.4
9.2.2 Outcomes? (e.g. date of occurrence, multiple event, severity measures related to event)				9.4
9.2.3 Covariates and other characteristics? (e.g., age, sex, clinical and drug use history, co-morbidity, co-medications, lifestyle)				9.4
9.3 Is a coding system described for:				
9.3.1 Exposure? (e.g., WHO Drug Dictionary, Anatomical Therapeutic Chemical (ATC) Classification System)				9.4
9.3.2 Outcomes? (e.g., International Classification of Diseases (ICD), Medical Dictionary for Regulatory Activities (MedDRA))				9.4
9.3.3 Covariates and other characteristics?				9.4

Section 9: Data sources	Yes	No	N/A	Section Number
9.4 Is a linkage method between data sources described? (e.g., based on a unique identifier or other)				9.4

Comments:

--

Section 10: Analysis plan	Yes	No	N/A	Section Number
10.1 Are the statistical methods and the reason for their choice described?				9.7
10.2 Is study size and/or statistical precision estimated?				9.5
10.3 Are descriptive analyses included?				9.7
10.4 Are stratified analyses included?				9.7.7
10.5 Does the plan describe methods for analytic control of confounding?				
10.6 Does the plan describe methods for analytic control of outcome misclassification?				9.7.6
10.7 Does the plan describe methods for handling missing data?				9.7.5
10.8 Are relevant sensitivity analyses described?				9.7.6

Comments:

--

Section 11: Data management and quality control	Yes	No	N/A	Section Number
11.1 Does the protocol provide information on data storage? (e.g., software and IT environment, database maintenance and anti-fraud protection, archiving)				9.6
11.2 Are methods of quality assurance described?				9.8
11.3 Is there a system in place for independent review of study results?				9.8

Comments:

--

Section 12: Limitations	Yes	No	N/A	Section Number
12.1 Does the protocol discuss the impact on the study results of:				
12.1.1 Selection bias?				9.9
12.1.2 Information bias?				

22195; XAPAEDUS; v 2.1, 16 NOV 2022;

Page 51 of 59

based on template version 9

Section 12: Limitations	Yes	No	N/A	Section Number
12.1.3 Residual/unmeasured confounding? (e.g., anticipated direction and magnitude of such biases, validation sub-study, use of validation and external data, analytical methods).				
12.2 Does the protocol discuss study feasibility? (e.g., study size, anticipated exposure uptake, duration of follow-up in a cohort study, patient recruitment, precision of the estimates)				9.4.1, 9.5.2

Comments:

Section 13: Ethical/data protection issues	Yes	No	N/A	Section Number
13.1 Have requirements of Ethics Committee/ Institutional Review Board been described?				9.4, 10
13.2 Has any outcome of an ethical review procedure been addressed?				
13.3 Have data protection requirements been described?				10

Comments:

Section 14: Amendments and deviations	Yes	No	N/A	Section Number
14.1 Does the protocol include a section to document amendments and deviations?				5

Comments:

Section 15: Plans for communication of study results	Yes	No	N/A	Section Number
15.1 Are plans described for communicating study results (e.g., to regulatory authorities)?				12
15.2 Are plans described for disseminating study results externally, including publication?				12

Comments:

Name of the main author of the protocol: _____ Date: dd/Month/year

Signature:

